7.3 Blinding

Double blinding of study drug, adalimumab vis-à-vis abatacept, is not feasible due to logistical barriers around repackaging adalimumab as well as the expected differences in injection-site reactions. Both of these together make effective blinding of the patients to the randomized drug assignment impractical and unsustainable. The nature and frequency of adalimumab-associated injection-site reactions make blinding investigators responsible for clinical care unsustainable under usual practices. It is possible, however, to preserve the objectivity of clinical assessments with the following strategy that has been designed to establish and maintain a single-blinded assessor for clinical endpoints throughout the study. This will require a minimum of 3 individuals: a blinded Clinical Assessor, an unblinded Study Research Coordinator, and an unblinded physician investigator/sub-investigator to complete/approve the case report form (CRF).

Clinical Assessors will be blinded to treatment allocation so as to preserve the objectivity of study-related assessments (tender and swollen joint count, Physician's Global Assessment of Disease Activity [PGA], AE causality assessment) and routine clinical care (laboratory result

review, medication adjustment). To preserve blinding, they must be shielded from treatment allocation throughout the entire study. This will be the responsibility of the Study/Research Coordinators who need not be blinded to treatment allocation. At the beginning of each study visit throughout the study duration, the participant should be reminded that the Clinical Assessor is blinded to treatment allocation and that care must be taken to prevent revealing treatment allocation. They should be instructed to:

- Not discuss study treatment by name
- Not discuss the color or use of the prefilled syringe
- Not discuss how often injections are performed
- Only discuss injection-site reactions of significant concern

To comply with requirements for CRF completion, a qualified physician who is an investigator or sub-investigator who is unblinded to study treatment assignment will be needed to promptly review, sign, and date the CRF.

The site should maintain 2 distinct sets of source documents: 1 set accessible to the unblinded site staff and 1 set for the blinded Clinical Assessor.

Care should be taken by the Study/Research Coordinator to retrieve any study treatment and sharps containers returned by the participant at the beginning of each visit to shield the assessor from inadvertent exposure to participant allocation. Similarly, study treatment dispensing should be done after blinded assessments. Both retrieval and dispensing of study treatment should be done in an area shielded from the blinded Clinical Assessor(s).

The joint count assessment should be performed after completion of the patient-reported outcomes (PROs), vital sign assessment, and AE assessment. The Clinical Assessor will similarly be reminded at the beginning of each study visit throughout the study duration that they are performing a blinded-assessment for the study and to not ask question or elicit comments that may reveal treatment allocation as outlined above. Every effort must be made to ensure the same evaluator(s) will complete the assessment for each participant. If the usual evaluator is not available, another trained evaluator blinded to study treatment allocation for the participant may perform the clinical assessment. In the event that no blinded evaluator is available during the study visit, blinded clinical assessment measures (tender and swollen joint counts and PGA) should not be reported.

In cases of accidental unblinding of blinded staff, contact the Clinical Trial Physician/Medical Monitor and ensure every attempt is made to preserve the blind. The purpose of this is to review options to continue blinded assessments and review site processes to prevent additional unblinding.

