All participants who discontinue study treatment should comply with protocol-specified follow-up procedures as outlined in [Section 2](#). The only exception to this requirement is when a participant withdraws consent for all study procedures including post-treatment study follow-up or loses the ability to consent freely (ie, is imprisoned or involuntarily incarcerated for the treatment of either a psychiatric or physical illness).

If study treatment is discontinued prior to the participant's completion of the study, the reason for the discontinuation must be documented in the participant's medical records and entered on the appropriate CRF page.

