8.2 Discontinuation From the Study

Participants who request to discontinue study treatment will remain in the study and must continue to be followed for protocol-specified follow-up procedures. The only exception to this is when a participant specifically withdraws consent for any further contact with him/her or persons previously authorized by participant to provide this information.

- Participants should notify the investigator of the decision to withdraw consent from future follow-up **in writing**, whenever possible.
- The withdrawal of consent should be explained in detail in the medical records by the investigator, as to whether the withdrawal is from further treatment with study treatment only or also from study procedures and/or post-treatment study follow-up, and entered on the appropriate CRF page.
- In the event that vital status (whether the participant is alive or dead) is being measured, publicly available information should be used to determine vital status only as appropriately directed in accordance with local law.
- If the participant withdraws consent for disclosure of future information, the Sponsor may retain and continue to use any data collected before such a withdrawal of consent.

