10.2 Populations for Analyses

The populations for the purpose of analyses are defined in Table 10.2-1.

Table 10.2-1: Populations for Analyses

Population	Description
Enrolled	All participants who sign informed consent form.
Modified Intent-to-treat Analysis Population	All randomized participants who receive at least 1 dose of study medication. This population will exclude participants who are randomized, but not treated. Analyses using the mITT analysis population will group the participants according to the treatment group to which they are randomized. All efficacy analyses will use the mITT population.
Intent-to-treat Population	All randomized participants, also those who are never treated. Participants who were randomized and never treated and did not return for any assessments after discontinuation (ie, lost to follow-up or withdrew consent) will be excluded from the ITT analysis population. This population may be used for a sensitivity analysis of the primary endpoint. Analyses using the ITT analysis population will group the participants according to the treatment group to which they are randomized.
Per-protocol Analysis Population	All randomized participants who receive at least 1 dose of study medication, excluding the participants with relevant protocol deviations. Relevant protocol deviations are those that potentially may impact the primary efficacy outcome. The criteria for relevant protocol deviations will be defined in the SAP. Analyses using the PP analysis population will group the participants according to the treatment group to which they are randomized.
As-treated Analysis Population	All participants who receive at least 1 dose of study medication. Analyses using the as-treated analysis population will group the participants on an as-randomized basis unless a participant received the incorrect medication for the entire period of treatment. In that case, the participant will be analyzed in the treatment group associated with the incorrect medication they received (“as-treated”). The as-treated analysis population will be used for safety analyses of the SBTP.
Cumulative Abatacept Population	All randomized participants who receive at least 1 dose of abatacept during the SBTP and/or the OLTP. All participants of the as-treated population will be included, except for participants treated with adalimumab in the SBTP who never entered the OLTP.
Subgroup of SE+ Participants	The subgroup of participants that are SE+ at baseline.

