10.3.1 Efficacy Analyses

Hierarchical testing of the primary and key secondary endpoints, as described in [Section 10.1](#), will be applied. P-values will be presented for the treatment comparisons of the primary and key secondary endpoints. Statistical analysis methods for efficacy analyses are provided in Table 10.3.1-1.

Table 10.3.1-1: Efficacy Statistical Analyses

Endpoint	Statistical Analysis Methods
Proportions	The binary efficacy endpoints (eg, the proportion of participants meeting ACR50 response at Week 24) will be analyzed with a logistic regression including treatment in the model. The OR along with its 95% CI will be provided. A missing responder value at Day 169 due to discontinuation or for other reasons will be imputed as a nonresponder. For analysis of variables in the overall population (SE+ and SE-), the stratification variable SE +/- will also be included as a factor in logistic regression model. For analysis of proportions that are based on a cutoff value of continuous variable (eg, remission defined as DAS28-CRP < 2.6) for which a corresponding value is measured at baseline (baseline DAS28-CRP measurement), the analysis model will also include the continuous baseline covariate.
Mean Change From Baseline	Mean changes from baseline in continuous variables will be analyzed using a longitudinal repeated measures analysis. The model will include the fixed categorical effects of treatment, day (is a windowed time point), stratification variable SE +/- (as appropriate), treatment-by-day interaction, and covariate of corresponding baseline and baseline-by-day interaction. An unstructured covariance matrix will be used to represent the correlation of the repeated measures within each participant. The parameter estimations will be based on the assumption of data being MAR and using the method of REML. The difference in adjusted LSMEANS between abatacept and adalimumab at the primary time point, Week 24, and corresponding 95% CI will be provided. For the key secondary variable of mean change from baseline at Week 24, the P-value will be based on the longitudinal model.

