APPENDIX 14 RA DISEASE ACTIVITY DEFINITIONS

American College of Rheumatology Core Data Set

ACR core data set component	Validated Measurement Tool
Tender joint count	Standardized 68 joint count
Swollen joint count	Standardized 66 joint count
Subject global assessment of pain	A 0-100mm visual analog scale
Subject global assessment of disease activity	A 0-100mm visual analog scale
Physician global assessment of disease activity	A 0-100mm visual analog scale
Subject assessment of physical function	Health Assessment Questionnaire (HAQ)
Acute phase reactant value	ESR (Westergren) and C-reactive protein

The ACR 20, ACR 50, or ACR 70 definition of improvement is a 20%, 50%, or 70% improvement, respectively, over baseline in tender and swollen joint counts (#1 and #2) and a 20%, 50%, or 70% improvement, respectively, in 3 of the 5 remaining core data set measures (components #3 to #7).

Disease Activity Index (DAS)28-CRP is calculated using the following formula:

$$\text{DAS28-CRP}(4) = 0.56 \cdot \sqrt{\text{TJC28}} + 0.28 \cdot \sqrt{\text{SJC28}} + 0.36 \cdot \ln(\text{CRP}+1) + 0.014 \cdot \text{GH} + 0.96$$

where t28 = number of painful joints from 28 joints, sw28 = number of swollen joints from 28 joints, CRP = c-reactive protein in mg/L, and GH = general health or patient's global assessment of disease activity on a 100 mm VAS

Simple Disease Activity Index (SDAI) is calculated using the following formula:

$$\text{TJC} + \text{SJC} + \text{PGA} + \text{MDGA} + \text{CRP}$$

Clinical Disease Activity Index (CDAI) is calculated using the following formula:

$$\text{TJC} + \text{SJC} + \text{PGA} + \text{MDGA}$$

(TJC = number of painful joints from 28 joints, SJC = number of swollen joints from 28 joints, PGA = patient global assessment on a visual analog scale 0-10 cm, MDGA = physician global assessment on a visual analog scale 0-10 cm, and CRP = c-reactive protein in mg/dL)

Boolean Remission is defined as:

Tender joint count \leq 1, Swollen joint count \leq 1, CRP \leq 1 mg/dL, patient global assessment \leq 1 (on 0 to 10 VAS scale).

**APPENDIX 15 JOINT COUNT ASSESSMENT COMPONENTS FOR DAS28
(RIGHT AND LEFT SIDE)**

Shoulder
Elbow
Wrist
MCP1
MCP2
MCP3
MCP4
MCP5
PIP1
PIP2
PIP3
PIP4
PIP5
Knee

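### Does scoring an on-treatment participant as a non-responder, only because no blinded joint assessor was available at Week 24, call for a change to the analysis plan?

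*Combined protocol and SAP*

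**What the plan says.** Section 7.3 protects the assessor blind strictly. A trained substitute who is also blinded may step in, but if "no blinded evaluator is available during the study visit, blinded clinical assessment measures (tender and swollen joint counts and PGA) should not be reported".

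Appendix 14 defines ACR50 as a 50% improvement, "respectively, over baseline in tender and swollen joint counts (#1 and #2"), together with the same improvement "in 3 of the 5 remaining core data set measures (components #3 to #7"). DAS28-CRP and CDAI both contain the 28-joint tender and swollen counts, and CDAI also contains the physician global.

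Table 10.3.1-1 gives the missing-data rule for binary endpoints: "A missing responder value at Day 169 due to discontinuation or for other reasons will be imputed as a nonresponder". There is no exception for administrative causes.

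Table 10.2-1 offers two alternative analysis sets. Of the ITT set it says: "This population may be used for a sensitivity analysis of the primary endpoint". For the per-protocol set: "The criteria for relevant protocol deviations will be defined in the SAP". Mean changes are analysed by a repeated-measures model under MAR.

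Section 8.1 requires that when treatment stops early "the reason for the discontinuation must be documented in the" medical records and on the CRF. Section 8.2 adds: "Participants who request to discontinue study treatment will remain in the study and must continue to be followed".

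**The concern.** Read together, these rules let a purely logistical event decide an efficacy outcome. A participant who is on treatment and doing well, but whose only blinded assessor is away on the Week 24 visit day, cannot be shown to be a responder. That participant counts as a failure for ACR50 in SE+ participants (test 1), DAS28-CRP remission (test 2), ACR50 in the full population (test 3) and CDAI remission (test 4). Only test 5, participant-reported pain, escapes.

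Nothing visible tests how much this matters. The optional ITT analysis changes who is included and leaves the imputation alone. The per-protocol set is attached to no endpoint. The MAR model covers means, not response rates. If such losses fell unevenly on the arms, the superiority result could depend partly on assessor availability, and a reader would want to see that it did not.

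**Working it through.** **1. Inputs.** Section 10.1 gives 150 per arm, about three quarters SE+, and two-sided 5% tests. 150 × 0.75 = 112.5, which agrees with the stated 112. Section 3.2.2 cites prior differences of 32 points (SE+ ACR50), 27 points (SE+ DAS28-CRP remission) and 25 points (ACR50, all participants). The planned response rates and powers are redacted and no rate of unassessed visits is given. The arm-level rates and loss rates below are therefore assumptions.

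**2. Weight of one case.** One misclassified responder moves an arm's rate by 1/112 = 0.89 points on the SE+ tests and by 1/150 = 0.67 points on test 3.

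**3. Equal loss.** Let m be the share lost in each arm, unrelated to response. Under the rule each rate becomes p(1 − m) and the difference becomes (1 − m)d. If the participants were excluded instead, the rates stay at p and the sample becomes 112(1 − m). Power is Φ(difference/SE − 1.96), with SE = √[pA(1 − pA)/n + pB(1 − pB)/n].

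Example, 65% versus 45%:
- No loss: SE = √(0.65×0.35/112 + 0.45×0.55/112) = 0.0651; 0.20/0.0651 = 3.07; power 86.7%.
- 5% loss under the rule: rates 61.75% and 42.75%; SE 0.0655; 0.19/0.0655 = 2.90; power 82.6%.
- 5% loss, excluded: n = 106.4; power 84.9%.

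| Assumed rates, n per arm | Loss | No loss | Under the rule | Excluded |
|---|---|---|---|---|
| 65% v 45%, 112 | 2% | 86.7% | 85.1% | 86.0% |
| 65% v 45%, 112 | 5% | 86.7% | 82.6% | 84.9% |
| 65% v 45%, 112 | 10% | 86.7% | 78.2% | 83.0% |
| 66% v 34%, 112 (32 points) | 5% | 99.90% | 99.76% | 99.85% |
| 50% v 23%, 112 (27 points) | 5% | 99.2% | 98.7% | 98.9% |
| 60% v 35%, 150 (25 points) | 5% | 99.4% | 98.9% | 99.2% |

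The rule's own cost is the gap between the last two columns. At 65% versus 45% it is 0.9, 2.3 and 4.8 points for 2%, 5% and 10% loss. Calculated exactly for the planned treatment-only logistic Wald test, it is smaller: 0.4, 1.7 and 3.9 points. With no true difference (50% in both arms) and 5% equal loss, the chance of a false win for abatacept is 2.6%, the same as with no loss.

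**4. Unequal loss.** The bias in the difference is pADA × lossADA − pABA × lossABA. At 65% versus 45%, each point of loss on abatacept alone shrinks the difference by 0.65 points; on adalimumab alone it widens it by 0.45. With equal true rates of 40% to 60% and 5% loss on one arm only, a spurious 2.0 to 3.0 points appears (0.05 × 40% to 0.05 × 60%), and two-sided rejection rises from 5.0% to between 6.1% and 7.4% (pooled-variance normal approximation).

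**5. How the loss could arise.** Three provisions stand in the way: the blinded substitute (Section 7.3), booking visits around the assessor (Section 9.1.2) and the ±3-day Week 24 window (Table 2-2). Loss needs every eligible blinded assessor to be unavailable across that window. Even 5% would mean 0.05 × 112 = 5.6 SE+ participants per arm.

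**6. What the report can show.** Treatment discontinuations and their reasons are on the CRF. On-treatment participants with no Week 24 counts are therefore the missing cases minus the discontinued ones. They can be counted by arm, and best-case and worst-case bounds can be run over them, without any new data field.

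**The case for a change.** The best case for acting is that imbalance is plausible on the protocol's own reasoning. Section 7.3 says adalimumab injection-site reactions make it unsustainable to blind the treating investigators, and participants may still raise reactions of significant concern with the assessor. An accidentally unblinded assessor with no replacement means no reported counts. Losses by that route would fall more on adalimumab, and scoring them as failures would favour abatacept. Non-responder imputation is then not automatically conservative. Section 9.1.2 also expects the substitute to have examined the participant with the first assessor, which narrows last-minute cover. A reason code and a tipping-point analysis would cost little.

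Part of this stands. The scoring consequence is real, the direction of bias under unequal loss is as described, and a table of missing Week 24 responder status by reason and arm would be good reporting. But the mechanism is inferred: no document gives a loss rate or shows an imbalance. The proposal would keep non-responder imputation as the main analysis, so it alleges no error there. Missing-data sensitivity analyses and CRF reason fields normally sit in a SAP and CRF, which are not supplied here, and part of Section 10.3.3 is redacted. A reason code would narrow the set of cases to examine, but a bounding analysis does not need it.

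**Conclusion.** No change to the plan follows. The rules do combine as described, but withholding unblinded joint counts and counting unproven response as non-response is a fair trade-off in a trial where only the assessor is blinded. Reporting unblinded counts would put bias into the endpoint to recover a few observations.

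Under equal loss the effect is attenuation only: negligible at the differences the plan cites, and about 2 points of power beyond losing the participants at an assumed 20-point difference with 5% loss. Unequal loss could bias the result either way, but nothing in the documents points to a material amount, and the affected participants can be identified and bounded from data already required. What remains is a supportive analysis and a table that analysts would ordinarily supply.

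This rests on the loss being rare, as the safeguards suggest, and on assumed response rates, because the planned ones are redacted. A visible imbalance between arms in on-treatment participants without Week 24 counts would be the reason to look again.

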7.4 Dosage Modification

7.4.1 Dose Modifications for Abatacept

7.4.1.1 Dose Modifications for Abatacept in the Absence of Adverse Events

Participants should complete their scheduled SC injections as described above. Participants who miss the dose window (± 3 days) should skip the SC injection and wait until the next targeted administration day.

7.4.1.2 Dose Modifications for Abatacept Due to Adverse Events

If abnormal laboratory test results or clinical AEs indicate toxicity that, in the judgment of the investigator, could place the participant at risk, study drug administration should be interrupted. If drug interruption exceeds 14 days, the investigator should notify the Sponsor's Clinical Trial Physician/Medical Monitor. Participants may receive further study medication treatment only if full resolution of the AE or abnormal laboratory finding is documented. **Under no circumstances should the dose of study drug be altered due to an AE.**

7.4.2 Dose Modifications for Adalimumab

7.4.2.1 Dose Modifications for Adalimumab in the Absence of Adverse Events

Participants should complete their scheduled SC injections as described above. Participants who miss the dose window (± 7 days) should skip the SC injection and wait until the next targeted administration day.

7.4.2.2 Dose Modifications for Adalimumab Due to Adverse Events

If abnormal laboratory test results or clinical AEs indicate toxicity that, in the judgment of the investigator, could place the participant at risk, study drug administration should be interrupted. If drug interruption exceeds 14 days, the investigator should notify the Sponsor's Clinical Trial Physician/Medical Monitor. Participants may receive further study medication treatment only if full resolution of the AE or abnormal laboratory finding is documented. **Under no circumstances should the dose of study drug be altered due to an AE.**

7.5 Preparation/Handling/Storage/Accountability

The IP should be stored in a secure area according to local regulations. It is the responsibility of the investigator to ensure that IP is only dispensed to study participants. The IP must be dispensed only from official study sites by authorized personnel according to local regulations.

The product storage manager should ensure that the study treatment is stored in accordance with the environmental conditions (temperature, light, and humidity) as determined by BMS. If concerns regarding the quality or appearance of the study treatment arise, the study treatment should not be dispensed and contact BMS immediately.

Study treatment not supplied by BMS will be stored in accordance with the package insert.

IP documentation (whether supplied by BMS or not) must be maintained that includes all processes required to ensure drug is accurately administered. This includes documentation of drug storage,

administration and, as applicable, storage temperatures, reconstitution, and use of required processes (eg, required diluents, administration sets).

